11.2 Secondary Analysis

A set of secondary objectives will also be examined. Additional factors that are potentially prognostic for complication rates will be examined as covariates in separate logistic regression analyses, to assess the sensitivity of the primary logistic regression model

results to additional covariate adjustment; factors include BMI (< 30 vs. \geq 30), age (< 65 vs. \geq 65 years), gender (male vs. female), diabetes mellitus, pathologic staging, pro-inflammatory cytokines known to affect appetite, background diet, current use of supplements, and any autoimmune disease. Also, in addition to the primary endpoint assessment of any complication at Day 30, we will assess the complication rate at day 90, as well as a composite endpoint with three levels (complications by Day 30, complication after Day 30 but by Day 90, and no complications by Day 90). In addition, we will examine the impact of SIM use on the Day 30 and Day 90 rates of infection (as determined by antibiotic use outside of prophylaxis), skeletal muscle mass, high-grade post-operative complications (Clavien Dindo Grades III–V), and readmission rates. To consider whether dropout may be non-random (i.e., informative), which could influence the results, a sensitivity analysis will be conducted that counts dropouts as events. Although death rates are anticipated to be low, 2-year overall survival by arm will be explored using Kaplan Meier curves, as will disease-free survival. The relationship between compliance and outcomes will be explored. A set of tertiary objectives will also be examined as indicated in [Appendix 18.2](#).

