1.2 Secondary Objectives

- a. To assess whether SIM use compared to ONS reduces late-phase post-operative complications within 90 days after scheduled RC.
- b. To assess whether SIM use compared to ONS reduces infections.
- c. To assess whether SIM use compared to ONS reduces skeletal muscle wasting.
- d. To assess whether SIM use compared to ONS reduces high grade post-operative complications.
- e. To assess whether SIM use compared to ONS reduces readmission rates.
- f. To assess whether SIM use compared to ONS improves quality of life.
- g. To assess whether SIM use compared to ONS improves disease-free survival after surgery and overall survival.

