Poor nutritional status is associated with higher complication rates after RC. (9,10,11) Specialized Immunonutrition (SIM) is fortified with nutrients (L-arginine, omega-3 fatty acids, dietary nucleotides, and vitamin A) that have immediate effects on immune and inflammatory responses, muscle sparing, and wound healing after surgery. In a randomized pilot trial of 29 patients, we found that giving SIM before and after RC reduced post-operative complications by 33% and most notably, reduced infections by 39% compared to an identical Oral Nutrition Support (ONS) lacking the immuno-modulators. (12) After RC, the SIM intervention significantly restrained the expansion of myeloid derived suppressor cells (MDSC), dampedened the post-surgical inflammatory response with a reduced magnitude of IL-6 elevation, and reduced muscle wasting by 10% compared to ONS. (13,14) Using perioperative SIM may benefit patients undergoing RC in a way that standard nutrition supplementation cannot. While the results of our pilot study are encouraging in that they show SIM improves immune response, a larger clinical trial is needed to definitively confirm whether SIM can significantly reduce post-operative complications. (15) A reduced post-operative complication rate is the key surgical outcome that would influence adoption of a new intervention aimed at improving the safety of RC.

Bladder cancer is prevalent and treatable, but morbidity, recurrence, and mortality are high. BCa is the fourth leading cancer in men, the sixth most common cancer in the United States, and has the highest lifetime treatment cost of all cancers. (16,17,18) Furthermore, up to 30% of all newly diagnosed patients present with muscle-invasive BCa. (19) The American Society of Clinical Oncology recently endorsed treatment guidelines for muscle-invasive BCa to include neoadjuvant

chemotherapy followed by radical cystectomy (RC). (20, 21) Unfortunately, RC is associated with high rates of post-operative complications (66%), infections (25%), and cancer recurrence (34%). (22, 23, 24) Ninety-day mortality rates are 7%. (25)

[figure not shown]

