7.11 Follow-Up Period

All patients will be followed for 3 years after radical cystectomy surgery or until death, whichever occurs first. See [Section 9.0](#) and [Section 14.4i](#) for follow-up and forms submission guidelines. See COVID-19 Guidance in [Section 7.13](#).

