- ^G The Scored Patient-Generated Subjective Global Assessment (PG-SGA) will be completed by the patient and the clinician (see [Section 7.1a](#)).
- ^H Includes recurrence and vital status at Months 3, 6, 9, 12, 18, 24 and 36 months after radical cystectomy surgery or until death. See [Section 14.4j](#). See COVID-19 Guidance in [Section 7.13](#).
- ^J Day 30 visit to take place within 7 days before or after Day 30 (after surgery date). Day 90 visit to take place within 7 days before or after Day 90 (after surgery date).
- ^K **Because blood samples are required to be collected and shipped on Day 2 following surgery (see Section 15.1), surgery should take place on a Monday, Tuesday, or Wednesday.**

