10.3 Disease-Free Survival

From date of surgery to date of first documentation of relapse/recurrence or death due to any cause. Patients last known to be alive without report of relapse/recurrence are censored at date of last contact.

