10.4 Overall Survival

From date of randomization to date of death due to any cause. Patients last known to be alive are censored at their last contact date.

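### The survival objective is comparative and data run to 36 months, but Section 11.2 names only an exploratory 2-year overall survival summary and no between-arm effect estimate

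*Combined protocol and SAP*

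**What the plan says.** The objective (Section 1.2, item g) is worded as a comparison with no time limit: "To assess whether SIM use compared to ONS improves disease-free survival after surgery and overall survival".

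The data schedule supports a 3-year horizon. Section 7.11 says "All patients will be followed for 3 years after radical cystectomy surgery or until death, whichever occurs first", and the calendar footnote in Section 9.0 reads "Includes recurrence and vital status at Months 3, 6, 9, 12, 18, 24 and 36 months after radical cystectomy surgery or until death".

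The endpoint definitions have no 2-year cut-off. Overall survival (Section 10.4) runs "From date of randomization to date of death due to any cause". Disease-free survival (Section 10.3) runs "From date of surgery to date of first documentation of relapse/recurrence or death due to any cause". Both censor at last contact.

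The analysis text is half a sentence in Section 11.2, prefaced by "Although death rates are anticipated to be low": "2-year overall survival by arm will be explored using Kaplan Meier curves, as will disease-free survival". By contrast, Section 11.1 gives the primary endpoint a logistic model adjusted for the three stratification factors.

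**The concern.** The objective, the definitions and the visit schedule all point to a between-arm comparison over 36 months. The analysis section describes a 2-year summary of overall survival by arm, with disease-free survival handled the same way but with no stated horizon. No hazard ratio, difference in survival, confidence interval or test is named.

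Two things follow. First, a 2-year overall survival estimate takes no information from deaths in year 3, although the trial follows patients to record them. Second, curves without an effect measure and interval do not tell the reader how large a benefit or harm remains compatible with the data. In a trial of this size, that interval is the most useful survival result available. Leaving the horizon and the model open also means they could be chosen after the curves have been seen.

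**Working it through.** **The plan's own figure.** The documents give no event count, survival rate or power for either survival endpoint. The only sample size is for 30-day complications (Section 11.1), and it reproduces. Inputs are 65% in the control arm, a 23-point reduction diluted by 5% non-adherence (0.65 − 0.95 × 0.23 = 0.4315), one-sided alpha 0.05, 80% power and continuity correction. The result is 73 per arm, or 146 in total; 146/0.77 = 189.6, taken as 190; 190/0.95 = 200. So N = 200 is fixed by an endpoint unrelated to survival.

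**Share of 3-year deaths falling after year 2.** With S(t) for survival at t years, the share is [S(2) − S(3)] / [1 − S(3)]. S(3) and the shape of the hazard are assumptions. The only mortality figure in the documents is 7% at 90 days (Section 2.0). Three hazard forms were used:

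- Constant hazard: S(2) = S(3)^(2/3).
- 7% dead by day 90, then constant hazard: with t0 = 90/365.25 years, λ = −ln(S(3)/0.93)/(3 − t0) and S(2) = 0.93 × exp(−λ(2 − t0)).
- Weibull with falling hazard, shape k: S(2) = exp(−H × (2/3)^k), where H = −ln S(3).

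| Hazard assumed | S(3) assumed | Share after year 2 |
|---|---|---|
| Constant | 0.50, 0.65, 0.80, 0.95 | 26.0%, 28.7%, 30.9%, 32.8% |
| 7% by day 90, then constant | 0.50, 0.65, 0.75, 0.85 | 25.3%, 25.8%, 24.4%, 18.8% |
| Weibull, k = 0.8 | 0.50, 0.70, 0.90 | 21.2%, 24.2%, 26.7% |
| Weibull, k = 0.7 | 0.50, 0.70, 0.90 | 18.7%, 21.5%, 23.7% |
| Weibull, k = 0.5 | 0.50, 0.70, 0.90 | 13.6%, 15.8%, 17.6% |

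Worked line, constant hazard, S(3) = 0.65: S(2) = 0.65^(2/3) = 0.750, so the share is (0.750 − 0.650)/(1 − 0.650) = 28.7%. The overall range is about 14% to 33%. A rising hazard would go higher (31% to 37% at k = 1.2, S(3) 0.50 to 0.90).

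**What it would buy.** Take N = 200, complete follow-up, constant hazard and S(3) = 0.65. Deaths are 200 × 0.25 = 50 by year 2 and 200 × 0.35 = 70 by year 3. By the Schoenfeld approximation with 1:1 allocation and one-sided alpha 0.05, power is Φ(√d × |ln HR|/2 − 1.645). At HR 0.70:

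- d = 50: Φ(1.26 − 1.645) = 35%.
- d = 70: Φ(1.49 − 1.645) = 44%.
- 80% power would need 195 deaths.

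With 70 deaths the standard error of the log hazard ratio is about 2/√70 = 0.239. An estimate of 1.0 would therefore carry a 95% interval of about exp(±1.96 × 0.239) = 0.63 to 1.60. That is wide, but it is a statement the planned curves do not make.

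**The case against.** The best defence is that this is an exploratory analysis in a trial sized on 30-day complications. The plan expects few deaths, the curves are drawn by arm (so a descriptive comparison is planned), and power is low at either horizon. All of that stands. No main conclusion of the trial depends on this change.

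Several stronger readings are tempting but not supported:

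- **That data after month 24 are discarded.** The definitions censor at last contact, so Kaplan-Meier curves can run to 36 months and display the later events. What is missing is a stated horizon and an effect estimate that uses them.
- **That disease-free survival is also cut at 2 years.** The 2-year label is attached to overall survival. For disease-free survival the horizon is simply unstated.
- **That a quarter to a third of deaths are lost.** That needs a constant hazard, which the documents do not give. Their 7% at 90 days suggests early deaths weigh heavily; building it in gives 19% to 26%.
- **That the plan loses a known amount of precision.** A 3-year hazard ratio would have a standard error about 7% smaller than a 2-year one (1 − √0.86) if the share is 14%, and about 18% smaller (1 − √0.67) if it is 33%. The plan contains neither hazard ratio, so this is not a loss against what is planned.
- **That the analysis cannot address arginine and recurrence.** Recurrence is captured by disease-free survival and assessed to month 36. Section 2.0 concludes that the evidence does not support a tumour-promoting effect and sets no long-term safety question for the survival analysis.

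Stratifying a Cox model on three binary factors would also create eight strata for perhaps 50 to 70 deaths or fewer. Covariate adjustment is the safer form.

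**Conclusion.** The mismatch is real and rests on the text alone: a comparative objective and 36 months of data meet an analysis that specifies a 2-year overall survival summary by arm, an unstated horizon for disease-free survival, and no effect estimate or interval.

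Its size can only be bracketed. Roughly 15% to a third of the deaths by 3 years would not contribute to a 2-year overall survival estimate, assuming a constant or falling hazard and 3-year survival between 0.50 and 0.95. Loss to follow-up that is early and unrelated to death would scale the death counts but not this share. The importance is low: it is a cheap improvement to an exploratory analysis and leaves the primary analysis untouched.

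**What to change.** Replace the survival wording in Section 11.2 with a sentence to this effect: overall and disease-free survival will be compared between arms using all follow-up to 36 months, by a Cox model adjusted for planned diversion type, prior neoadjuvant therapy and baseline nutrition status, reporting the hazard ratio with its confidence interval; Kaplan-Meier estimates at 2 and 3 years will be shown by arm; these analyses are exploratory. Use covariate adjustment rather than eight-way stratification if deaths are few.

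No new patients, visits or data items are needed. The cost is that the final survival report waits for the month-36 data already in the schedule. Power for overall survival stays low, so the result should be read through its interval and not as a test.

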11.3 Data and Safety Monitoring Committee

A Data and Safety Monitoring Committee will oversee the conduct of the study. The Committee consists of four members from outside of the SWOG, 3 SWOG members, 3 non-voting representatives from the National Cancer Institute (NCI), and the Group Statistician (non-voting). The members of this Committee will receive confidential reports every 6 months from the SWOG Statistical Center, and will meet at the Group's bi-annual meetings as necessary. The Committee will be responsible for decisions regarding possible termination and/or early reporting of the study.

12.0 DISCIPLINE REVIEW

Discipline Review is not required for this study.

13.0 REGISTRATION GUIDELINES

13.1 Registration Timing

Study sites must meet requirements and have approval for study participation before registering patients to the study (See [Section 13.2b.3](#) and [Section 18.7](#)).

Patients must be registered prior to initiation of treatment (at least 10 days and no more than 28 days prior to planned surgery).

13.2 Investigator/Site Registration

Prior to the recruitment of a patient for this study, investigators must be registered members of a Cooperative Group. Each investigator must have an NCI investigator number and must maintain an "active" investigator registration status through the annual submission of a complete investigator registration packet to CTEP.

a. CTEP Registration Procedures

Food and Drug Administration (FDA) regulations and National Cancer Institute (NCI) policy require all individuals contributing to NCI-sponsored trials to register

and to renew their registration annually. To register, all individuals must obtain a Cancer Therapy Evaluation Program (CTEP) Identity and Access Management (IAM) account at <https://ctepcore.nci.nih.gov/iam>. In addition, persons with a registration type of Investigator (IVR), Non-Physician Investigator (NPIVR), or Associate Plus (AP) (i.e., clinical site staff requiring write access to OPEN, Rave, or acting as a primary site contact) must complete their annual registration using CTEP's web-based Registration and Credential Repository (RCR) at <https://ctepcore.nci.nih.gov/rrc>.

RCR utilizes five-person registration types.

- IVR — MD, DO, or international equivalent;
- NPIVR — advanced practice providers (e.g., NP or PA) or graduate level researchers (e.g., PhD);
- AP — clinical site staff (e.g., RN or CRA) with data entry access to CTSU applications (e.g., Roster Update Management System (RUMS), OPEN, Rave,);
- Associate (A) — other clinical site staff involved in the conduct of NCI-sponsored trials; and
- Associate Basic (AB) — individuals (e.g., pharmaceutical company employees) with limited access to NCI-supported systems.

RCR requires the following registration documents:

Documentation Required	IVR	NPIVR	AP	A	AB
FDA Form 1572	✓	✓			
Financial Disclosure Form	✓	✓	✓		
NCI Biosketch (education, training, employment, license, and certification)	✓	✓	✓		
GCP training	✓	✓	✓		
Agent Shipment Form (if applicable)	✓				
CV (optional)	✓	✓	✓		

An active CTEP-IAM user account and appropriate RCR registration is required to access all CTEP and Cancer Trials Support Unit (CTSU) websites and applications. In addition, IVRs and NPIVRs must list all clinical practice sites and Institutional Review Boards (IRBs) covering their practice sites on the FDA Form 1572 in RCR to allow the following:

- Addition to a site roster;
- Assign the treating, credit, consenting, or drug shipment (IVR only) tasks in OPEN;
- Act as the site-protocol Principal Investigator (PI) on the IRB approval; and
- Assign the Clinical Investigator (CI) role on the Delegation of Tasks Log (DTL).

In addition, all investigators act as the Site-Protocol PI, consenting/treating/drug shipment, or as the CI on the DTL must be rostered at the enrolling site with a participating organization (i.e., Alliance).

Additional information is located on the CTEP website at <https://ctep.cancer.gov/investigatorResources/default.htm>. For questions, please contact the **RCR Help Desk** by email at [contact].

b. CTSU Registration Procedures

This study is supported by the NCI Cancer Trials Support Unit (CTSU).

1. **IRB Approval:**

For CTEP and Division of Cancer Prevention (DCP) studies open to the National Clinical Trials Network (NCTN) and NCI Community Oncology Research Program (NCORP) Research Bases after March 1, 2019, all U.S.-based sites must be members of the NCI Central Institutional Review Board (NCI CIRB). In addition, U.S.-based sites must accept the NCI CIRB review to activate new studies at the site after March 1, 2019. Local IRB review will continue to be accepted for studies that are not reviewed by the CIRB, or if the study was previously open at the site under the local IRB. International sites should continue to submit Research Ethics Board (REB) approval to the CTSU Regulatory Office following country-specific regulations.

Sites participating with the NCI CIRB must submit the Study Specific Worksheet for Local Context (SSW) to the CIRB using IRBManager to indicate their intent to open the study locally. In order for the SSW approval to be processed, the Signatory Institution must inform the CTSU which CIRB-approved institutions aligned with the Signatory Institution are participating in the study. The NCI CIRB's approval of the SSW is automatically communicated to the CTSU Regulatory Office, but sites are required to contact the CTSU Regulatory Office at [contact] to establish site preferences for applying NCI CIRB approvals across their Signatory Network. Site preferences can be set at the network or protocol level. Questions about establishing site preferences can be addressed to the CTSU Regulatory Office by emailing the email address above or calling [name].

In addition, the Site-Protocol Principal Investigator (PI) (i.e. the investigator on the IRB/REB approval) must meet the following criteria to complete processing of the IRB/REB approval record:

- Holds an Active CTEP status;
- Rostered at the site on the IRB/REB approval (*applies to US and Canadian sites only*) and on at least one participating roster;
- If using NCI CIRB, rostered on the NCI CIRB Signatory record;
- Includes the IRB number of the IRB providing approval in the Form FDA 1572 in the RCR profile; and
- Holds the appropriate CTEP registration type for the protocol.

Additional Requirements

Assignment of site registration status in the CTSU Regulatory Support System (RSS) uses extensive data to make a determination of whether a site has fulfilled all regulatory criteria including but not limited to the following:

- An active Federal Wide Assurance (FWA) number;
- An active roster affiliation with the Lead Protocol Organization (LPO) or a Participating Organization (PO); and
- Compliance with all protocol-specific requirements (PSRs).

2. Downloading Site Registration Documents:

Download the site registration forms from the protocol-specific page located on the CTSU members' website. Permission to view and download this protocol and its supporting documents is restricted and is based on person and site roster assignment. To participate, the institution and its associated investigators and staff must be associated with the LPO or a PO on the protocol.

- Log on to the CTSU members' website (<https://www.ctsu.org>) using your CTEP-IAM username and password;
- Click on *Protocols* in the upper left of your screen
- Enter the protocol number in the search field at the top of the protocol tree, or
- Click on the *By Lead Organization* folder to expand, then select SWOG, and protocol number **S1600**
- Click on *Documents*, select *Site Registration*, and download and complete the forms provided. (Note: For sites under the CIRB initiative, IRB data will load automatically to the CTSU as described above.)

3. Requirements For S1600 Site Registration:

- IRB approval (For sites not participating via the NCI CIRB; local IRB documentation, an IRB-signed CTSU IRB Certification Form, Protocol of Human Subjects Assurance Identification/IRB Certification/Declaration of Exemption Form, or combination is accepted)
- Site must meet all five criteria listed on the **S1600** Site Requirements Form (see [Appendix 18.7](#)). This form must be completed and submitted to the CTSU Regulatory Office via the Regulatory Submission Portal on the CTSU website as a protocol specific requirement prior to registering any patients.

4. Submitting Regulatory Documents:

Submit required forms and documents to the CTSU Regulatory Office via the Regulatory Submission Portal on the CTSU website.

Regulatory Submission Portal: www.ctsu.org (members' area) → Regulatory Tab → Regulatory Submission

Institutions with patients waiting that are unable to use the Regulatory Submission Portal should alert the CTSU Regulatory Office immediately at [name] in order to receive further instruction and support.

5. Checking Your Site's Registration Status:

You can verify your site's registration status on the members' side of the CTSU website.

- Go to <https://www.ctsu.org> and log in to the members' area using your CTEP-IAM username and password
- Click on the Regulatory tab at the top of your screen

- Click on the Site Registration tab
- Enter your 5-character CTEP Institution Code and click on Go

Note: The status shown only reflects institutional compliance with site registration requirements as outlined above. It does not reflect compliance with protocol requirements for individuals participating on the protocol or the enrolling investigator's status with the NCI or their affiliated networks.

13.3 OPEN Registration Requirements

The individual registering the patient must have completed the appropriate SWOG Registration Worksheet. The completed form must be referred to during the registration but should not be submitted as part of the patient data.

The Oncology Patient Enrollment Network (OPEN) is a web-based registration system available on a 24/7 basis. OPEN is integrated with CTSU regulatory and roster data and with the Lead Protocol Organization (LPOs) registration/randomization systems or Theradex Interactive Web Response System (IWRS) for retrieval of patient registration/randomization assignment. OPEN will populate the patient enrollment data in NCI's clinical data management system, Medidata Rave.

Requirements for OPEN access:

- A valid CTEP-IAM account;
- To perform enrollments or request slot reservations: Be on a LPO roster, ETCTN Corresponding roster, or PO roster with the role of Registrar. Registrars must hold a minimum of an AP registration type;
- If a Delegation of Tasks Log (DTL) is required for the study, the registrar(s) must hold the OPEN Registrar task on the DTL for the site; and
- Have an approved site registration for a protocol prior to patient enrollment.

To assign an Investigator (IVR) or Non-Physician Investigator (NPIVR) as the treating, crediting, consenting, drug shipment (IVR only), or receiving investigator for a patient transfer in OPEN, the IVR or NPIVR must list the IRB number used on the site's IRB approval on their Form FDA 1572 in RCR. If a DTL is required for the study, the IVR or NPIVR must be assigned the appropriate OPEN-related tasks on the DTL.

Prior to accessing OPEN, site staff should verify the following:

- Patient has met all eligibility criteria within the protocol stated timeframes and the affirmation of eligibility on the Registration Worksheet has been signed by the registering investigator or another investigator designate. Site staff should refer to [Section 5.0](#) to verify eligibility.
- All patients have signed an appropriate consent form and HIPAA authorization form (if applicable).

Note: The OPEN system will provide the site with a printable confirmation of registration and treatment information. Please print this confirmation for your records.

OPEN will also ask additional questions that are not present on the SWOG Registration Worksheet. The individual registering the patient must be prepared to provide answers to the following questions:

- a. Institution CTEP ID
- b. Protocol Number
- c. Registration Step

- d. Treating Investigator
- e. Credit Investigator
- f. Patient Initials
- g. Patient's Date of Birth
- h. Patient SSN (SSN is desired, but optional. Do not enter invalid numbers.)
- i. Country of Residence
- j. ZIP Code
- k. Gender (select one):
 - Female Gender
 - Male Gender
- l. Ethnicity (select one):
 - Hispanic or Latino
 - Not Hispanic or Latino
 - Unknown
- m. Method of Payment (select one):
 - Private Insurance
 - Medicare
 - Medicare and Private Insurance
 - Medicaid
 - Medicaid and Medicare
 - Military or Veterans Sponsored NOS
 - Military Sponsored (Including Champus & Tricare)
 - Veterans Sponsored
 - Self-Pay (No Insurance)
 - No Means of Payment (No Insurance)
 - Other
 - Unknown
- n. Race (select all that apply):
 - American Indian or Alaska Native
 - Asian
 - Black or African American
 - Native Hawaiian or other Pacific Islander
 - White
 - Unknown

